Participant Disposition	
A detailed description of participant disposition will be provided, including a summary of the number and percentage of participants entered into the study and randomized, and number and percentage of participants who complete the study or discontinue, both overall and by reason for discontinuation. A summary of important protocol deviations will be provided.

Participant Characteristics	
Demographic data are collected and responded to demonstrate that the study population represents the target patient population. A summary of baseline participant characteristics, historical diagnoses, preexisting conditions, and prior therapies will be reported by treatment group using descriptive statistics. Other participant characteristics will be summarized by treatment group as deemed appropriate.

Concomitant Therapy	
Previous and concomitant medications will be summarized by treatment group and will be presented by Anatomical Therapeutic Chemical drug classes using the latest version of the WHO drug dictionary.

Treatment Compliance	No analyses are planned to assess treatment compliance, given that participants will receive study intervention directly from the investigator or designee at the study site, under medical supervision.
----------------------	--

Summary statistics for continuous measures will include sample size, mean, standard deviation, median, minimum, and maximum.

For categorical data, summary statistics will include sample size, frequency, and percentages. Percentages will be rounded to one decimal place. Unless otherwise specified, Fisher's exact test will be used for making treatment comparisons.

All statistical tests of treatment effects will be performed at two-sided significance levels of 0.05 and 0.10, respectively, unless otherwise specified. All p-values will be presented to three decimal places.

The Treatment Period is defined as the combination of Period 1 with double-blind treatment and Period 2.

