The time to onset of first treatment-emergent hypersensitivity during the Treatment Period and the duration of each treatment-emergent hypersensitivity during the Treatment Period will also be defined and calculated in the same way.

A by-patient listing of all treatment-emergent hypersensitivities will be provided.

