4.6.2.2. Infusion Site Reactions

Infusion site reactions will be defined using terms from the infusion site reactions high level term.

The frequency and percentage of patients with a treatment-emergent infusion site reaction will be summarized by treatment arm, maximum severity, SOC, and Preferred Term during Treatment Period.

The frequency and percentage of patients with infusion site reactions will be summarized by treatment arm and redness category (normal, noticeable but very mild redness, clearly red, bright red, and dark with some scar formation) during Treatment Period and during Treatment Period. Similarly, the frequency and percentage of patients with infusion site reactions will be summarized by treatment arm and swelling category (no bump, barely noticeable, clear bump but very thin, clear bump 1mm thick, clear bump 2mm thick or more) during Treatment. Finally, the frequency and percentage of patients with infusion site reactions will be summarized by treatment arm and pain category (none, mild, moderate and severe) during Treatment Period.

The duration of each treatment-emergent infusion site reaction during the Treatment will be defined and summarized in the same way as described for infectious AEs in Section 16.4.2.1.

A by-patient listing of treatment-emergent infusion site reactions will be provided.

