If a patient does not have a treatment-emergent infectious AE during the Treatment Period, they will be censored at the date of completion or early discontinuation from the Treatment Period. Kaplan-Meier estimates of the proportion of patients not yet experiencing their first treatment-emergent infectious AE at 1, 6, 12 and 24 weeks will be provided for each treatment arm. A Kaplan-Meier plot of the time to onset will be presented by treatment arm.

The duration of each treatment-emergent infectious AE during the Treatment Period will be defined as follows:

Duration of treatment-emergent infectious AE (in weeks) = (End date of AE – Start date of AE + 1) / 7.

If an AE has not ended by the date of completion or early discontinuation from the study, including the Post-Treatment Follow-up Period, it will be censored as of that date. Descriptive statistics for the duration of treatment-emergent infectious AEs will be summarized by treatment arm. If a patient has more than one treatment-emergent infectious AE during the Treatment Period, then each AE will contribute to the analysis. If a patient does not have a treatment-emergent infectious AE during the Treatment Period, they will not be included in the analysis.

By-patient listings of patients experiencing a treatment-emergent infectious AE, infection-related deaths, and treatment-emergent opportunistic infections will be provided. The listing will include the following: patient demographics (including geographic region), concomitant medication,

results for total leukocytes, lymphocytes and total B lymphocytes, event start and stop dates, study treatment start and end dates, and the event outcome.

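### Durations of infections still ongoing at study end are to be censored but summarised only with ordinary descriptive statistics, so the mean is too low whenever an event is unresolved

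*SAP*

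**What the plan says.** SAP 4.6.2.3 defines one duration per event: "Duration of treatment-emergent infectious AE (in weeks) = (End date of AE – Start date of AE + 1) / 7". The rule for unresolved events follows: "If an AE has not ended by the date of completion or early discontinuation from the study", with post-treatment follow-up counted as part of the study, "it will be censored as of that date". The next sentence gives the whole analysis: "Descriptive statistics for the duration of treatment-emergent infectious AEs will be summarized by treatment arm". SAP 4.1 says what that contains: "Summary statistics for continuous measures will include sample size, mean, standard deviation, median, minimum, and maximum". Nothing says how a censored value enters these statistics, and no count of ongoing events is requested.

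Earlier in the same section, time to first infection is also censored, but there the SAP plans "Kaplan-Meier estimates of the proportion of patients not yet experiencing their first treatment-emergent infectious AE at 1, 6, 12 and 24 weeks" and a Kaplan-Meier plot.

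The duration method is carried to two other event types. For infusion site reactions (SAP 4.6.2.2), duration "will be defined and summarized in the same way as described for infectious AEs", with a pointer to Section 16.4.2.1, which is not in this SAP. For hypersensitivities (SAP 4.6.2.1), duration "will also be defined and calculated in the same way", with no statement of which method is meant.

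**The concern.** A censored duration is a lower bound. If it is put into an ordinary mean, the bound is treated as the value, and the error can only go one way: events look shorter than they were. The events affected are those still unresolved when observation stops, which tend to be the long ones.

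These are safety statements about a new immune-modulating antibody. SAP 4.6.2.3 includes opportunistic infections and reactivation of tuberculosis or hepatitis, so some long events are plausible. A few of them can move a mean a good deal even when the share censored is small. A reader of the table could not tell, because the number of ongoing events is not to be shown beside it.

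**Working it through.** The documents state no duration, ongoing fraction or bias, so there is no figure of the plan's to reproduce. The check is what the planned mean and median would show if censored durations entered as complete.

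**Inputs from the documents**
- Treatment-emergent onset is judged against the first dose and Visit 10, Week 24 (SAP 4.6.2).
- Follow-up runs 12 further weeks, to Week 36 (SAP 1.2; Protocol 1.3).
- A completer is therefore observed for at least about 12 weeks, and at most 36, after a treatment-emergent onset.
- Protocol 7.2 expects discontinuation to be uncommon but gives no rate.

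**Assumptions**
- Onset is uniform over Weeks 0 to 24, so the available observation time C is uniform on 12 to 36 weeks.
- Durations are exponential with mean m = median / ln 2.
- In some scenarios 5% or 10% of infections are chronic, with median 26 weeks.
- 0%, 10% or 20% of participants leave early, at a uniform point after onset.

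**Mean, no early leavers.** For exponential durations:
- fraction censored p = (m/24) × [exp(−12/m) − exp(−36/m)]
- naive mean = m × (1 − p)

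Short infections, median 1.5 weeks: m = 1.5/0.693 = 2.16 and p = 0.0004. The naive mean is 2.16, so there is no visible bias.

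Chronic infections, median 26 weeks: m = 26/0.693 = 37.51 and p = (37.51/24) × (0.726 − 0.383) = 0.536. The naive mean is 37.51 × 0.464 = 17.39.

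Mixtures of the two:
- 5% chronic: true mean 0.95 × 2.16 + 0.05 × 37.51 = 3.93; naive mean 0.95 × 2.16 + 0.05 × 17.39 = 2.92. That is 26% low, with only 0.05 × 0.536 = 2.7% of events censored.
- 10% chronic: true mean 5.70, naive mean 3.69. That is 35% low, with 5.4% censored.

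A simulation of 1,000,000 events per scenario agrees: 2.93 against 3.94 (26% low) and 3.69 against 5.73 (36% low). With no chronic share, the naive mean is 15% low at a true median of 8 weeks and 45% low at 20 weeks.

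Part of the mixture deficit lies beyond any possible follow-up. Against the mean restricted to 36 weeks, which Kaplan-Meier can estimate, the naive mean is 1 − 2.93/3.21 = 9% low with 5% chronic and 1 − 3.69/4.27 = 14% low with 10% chronic.

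**Median** (simulated; bias of the naive median)

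| True median | No early leavers | 10% to 20% early leavers |
|---|---|---|
| about 1.5 to 3.4 weeks | 0% | 1% to 5% low |
| 8 to 12 weeks | 0% | 5% to 14% low |
| 20 weeks | 23% low (15.5 vs 20.0) | 27% to 30% low |

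The zeros follow from the design: if nobody is cut off before 12 weeks, a median of 12 weeks or less cannot move.

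**Kaplan-Meier on the same data.** It matched the true median in every scenario (20.0 where the naive median was 15.5) and the mean restricted to 36 weeks (4.27 against a true 4.27 with 10% chronic).

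**Resolved events only.** Suppose 20% of exponential durations are censored at a common time c. Then exp(−c) = 0.2, so c = 1.609 true means. The naive mean is 0.80 of the truth. The mean over resolved events is (0.8 − 0.2 × 1.609)/0.8 = 0.60 of the truth. Leaving the ongoing events out makes the bias worse.

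**The case against.** The SAP does not say that censored durations are treated as complete. That is correct: it gives no rule at all. The reading rests on the fact that every value is to be summarised by statistics that have no place for a censoring flag. The other possible reading, leaving ongoing events out, is more biased still, so the text needs a rule either way.

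The practical effect may be nil. If infections are short and few participants leave, nothing is censored and the mean is right. This stands, and it is why the size can be given only as a range over assumptions.

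The information is not lost. The by-patient listings in SAP 4.6.2.3 carry start and stop dates and outcome, and Protocol 8.3.3 follows adverse events of special interest to resolution or stabilisation. Both help, but neither corrects the summary table. The second means that the SAP's cut at study end could discard an end date that is later known.

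Three stronger readings are tempting, and the documents do not support them:
- That the median is generally biased. About 12 weeks of observation after the last treatment-emergent onset protects it unless participants leave early or typical durations are very long.
- That the bias differs by arm because only some participants are dosed after Week 14. Protocol 4.1 and 6.5.3 describe the others as stopping infusions and moving to standard of care, not as leaving, and the schedule makes only dosing in Weeks 16 to 24 conditional. Different follow-up by arm is not shown.
- That all adverse events of special interest are affected. Malignancy has no duration analysis (SAP 4.6.2.4), and for hypersensitivities the method is only apparently the same.

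**Conclusion.** The point holds for the mean and, where the longest event is unresolved, for the maximum. SAP 4.6.2.3 recognises that durations are censored and then names no summary that respects it, although it does so for onset a few lines earlier. The mean is understated whenever any event is ongoing, by an amount that depends on durations and withdrawal rates the documents do not give. Without early leavers, the assumed scenarios give about 0% for short infections and about 26% to 36% low with 5% to 10% chronic infections. These figures rest on uniform onset and exponential durations, and much of the deficit in the chronic scenarios lies beyond Week 36, where no method can recover it. The median is materially affected only with early withdrawal or typical durations beyond about 12 weeks.

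The consequence is limited. This is a descriptive safety output in a proof-of-concept study of about 80 participants, and no test, primary result or sample size uses it. It is worth correcting because the error in the mean is never upward and the correction is simple.

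**What to change.** In SAP 4.6.2.3, replace the descriptive summary of duration by the Kaplan-Meier median and quartiles with ongoing events censored, and report the number and percentage of events ongoing at censoring by arm. If a plain mean is kept, label it as an observed minimum duration. Do not use a mean over resolved events as the main summary. Where follow-up under Protocol 8.3.3 yields a resolution date after study end, use it in place of the censoring date.

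Apply the same rule in SAP 4.6.2.2, correcting the reference to Section 16.4.2.1, and in SAP 4.6.2.1, stating which definition and summary are meant.

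The cost is a few sentences of SAP text and one more call to Kaplan-Meier code that the section already needs for time to onset. Adverse event start and stop dates are already collected. Kaplan-Meier assumes that censoring is unrelated to how long the event would have lasted, so the count of ongoing events should stand beside it in any case.

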4.6.2.4. Malignancies

Malignancies will be defined using terms from the Malignant or unspecified tumors SMQ.

The frequency and percentage of patients with a treatment-emergent malignancy will be summarized by treatment arm, maximum severity, SOC, and Preferred Term during the Treatment Period. Exposure-adjusted incidence rates (per 100 patient years), as defined in Section 6.14.2.1, for each type of treatment-emergent malignancy will be presented by treatment arm, Preferred Term and time interval during the Treatment Period. Adverse events will be summarized under a particular time interval if they started or worsened on or after the interval start date and before the interval end date. Exposure-adjusted incidence rates will also be presented graphically by treatment arm and time interval.

A by-patient listing of treatment-emergent malignancies will be provided.

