4.6.2.1. Hypersensitivities

Hypersensitivities will be defined using the following terms:

- Anaphylactic reaction standardized MedDRA query (SMQ) excluding the Preferred Term Anaphylactic transfusion reaction
- Angioedema SMQ excluding the Preferred Terms Oedema neonatal and Peripheral oedema neonatal
- Severe cutaneous adverse reactions SMQ Narrow Search terms and the following Broad Search terms:
 - Drug eruption
 - Drug rash with eosinophilia and systemic symptoms
 - Lip exfoliation
 - Mucosal exfoliation
 - Penile exfoliation
 - Skin exfoliation

- Stomatitis
 - Tongue exfoliation
 - Vaginal exfoliation
- Additional Preferred Terms including:
 - Asphyxia
 - Dermatitis
 - Dermatitis allergic
 - Dermatitis atopic
 - Dermatitis contact
 - Diastolic hypotension
 - Eczema
 - Eosinophilic oesophagitis
 - Erythema nodosum
 - Hypotension
 - Immediate post-injection reaction
 - Injection related reaction
 - Orthostatic hypotension
 - Photosensitivity allergic reactions
 - Photosensitivity reaction
 - Presyncope
 - Rash vesicular
 - Reaction to drug excipients
 - Red man syndrome
 - Serum sickness
 - Serum sickness-like reaction
 - Syncope
 - Type II hypersensitivity
 - Type III immune-complex-mediated reaction
 - Type IV hypersensitivity reaction
 - Toxic skin eruption
 - Urticaria contact
 - Urticaria vesiculosa

The frequency and percentage of patients experiencing treatment-emergent hypersensitivities will be summarized by treatment arm, maximum severity, SOC, and Preferred Term during Treatment Period. The frequency and percentage of patients experiencing treatment-emergent hypersensitivities will also be summarized by treatment arm and timing category (immediate, acute reaction, delayed reaction or reaction after more than 15 days).

Exposure-adjusted incidence rates (per 100 patient years) of treatment-emergent hypersensitivities within the following time intervals will be calculated as detailed below.

- ≥ 0 to ≤ 6 weeks since the date of first injection:

Interval start date = Date of first injection,

Interval end date = Date of first injection + 42 days.

- > 6 to ≤ 12 weeks since the date of first injection:
Interval start date = Date of first injection + 43 days,
Interval end date = Date of first injection+ 84 days.
- ≥ 24 weeks since the date of first injection:
Interval start date = Date of first injection + 85,
No Interval end date, Treatment Period planned for 24 weeks

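### SAP 4.6.2.1 heads an interval that starts at first injection + 85 as 24 weeks or later, and the event rule in 4.6.2.4 and 4.6.2.5 leaves days + 42 and + 84 in no interval

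*SAP*

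**What the plan says.** SAP 4.6.2.1 (Hypersensitivities) sets out three intervals, each with a label and dates counted from the first injection.

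- First: "≥ 0 to ≤ 6 weeks since the date of first injection". It begins on the date of first injection, and "Interval end date = Date of first injection + 42 days".
- Second: "> 6 to ≤ 12 weeks since the date of first injection", with "Interval start date = Date of first injection + 43 days" and "Interval end date = Date of first injection+ 84 days".
- Third: "≥ 24 weeks since the date of first injection", with "Interval start date = Date of first injection + 85". No end date is given, and the text notes that the Treatment Period is planned to last 24 weeks.

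That section does not say how an event on a boundary date is assigned. SAP 4.6.2.4 (Malignancies) and 4.6.2.5 (Depression) do. Events count under an interval "if they started or worsened on or after the interval start date and before the interval end date". Both sections refer to Section 6.14.2.1 for the definition of the rates. The SAP has no such section, and the only interval dates it contains are those in 4.6.2.1.

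**The concern.** There are two separate defects.

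The first is visible within 4.6.2.1 alone: the third label does not match its start date. A table built from these definitions would report nearly all of Period 2 as time at or beyond 24 weeks. Participants who continue on LY3462817 have infusions scheduled at Weeks 16 and 20 (Protocol 1.3), so a reaction around either infusion would be shown as arising at 24 weeks or later.

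The second appears when the rule in 4.6.2.4 and 4.6.2.5 is applied to the 4.6.2.1 dates. The rule excludes the end date, but the next interval starts the day after it. The end date itself then belongs to neither interval, which contradicts the labels. A malignancy or depression event with onset on such a date would be missing from the interval-specific rates and from the plots based on them. Event counts in arms of about 40, 20 and 20 are likely to be small, so a programmer should not be left to guess the rule.

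**Working it through.** **Inputs.** Labels and dates of the three intervals: SAP 4.6.2.1. Assignment rule: SAP 4.6.2.4, with the same wording in 4.6.2.5. Planned Treatment Period of 24 weeks: SAP 4.6.2.1. Let d be the number of days after first injection.

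**Step 1. Labels against dates (weeks × 7).**

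| Label limit | Days implied | Date in SAP | Match |
|---|---|---|---|
| 6 weeks | 6 × 7 = 42 | + 42 (end of first) | yes |
| 12 weeks | 12 × 7 = 84 | + 84 (end of second) | yes |
| 24 weeks | 24 × 7 = 168 | + 85 (start of third) | no |

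The first two limits reproduce. The third does not: 85 / 7 = 12.14 weeks. Days that fall in the third interval but come before 24 weeks run from + 85 to + 167, and 167 − 85 + 1 = 83 days. Of the 84 days from + 85 to + 168, only + 168 fits the heading.

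**Step 2. Assignment of each day from 0 to 168 (169 days), rule as written: start ≤ d < end.**

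- First interval: d = 0 to 41, 42 days.
- Second interval: d = 43 to 83, 41 days.
- Third interval (no end): d = 85 to 168, 84 days.
- Sum: 42 + 41 + 84 = 167. Unassigned: 169 − 167 = 2 days, namely + 42 and + 84. No day falls in two intervals.

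The labels include both days, since each uses ≤ at its upper limit. Counting the day of first injection as day 1 only renames the missing dates as study days 43 and 85.

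**Step 3. Same enumeration with the end date included: start ≤ d ≤ end.**

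- 43 + 42 + 84 = 169. No day is unassigned and none is counted twice.

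**Step 4. Size of the gap.** If onset is uniform over the period (an assumption), the share of events on an unassigned date is 2 / 169 = 1.2% over days 0 to 168, or 2 / 85 = 2.4% over days 0 to 84.

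**The case against.** The best reply is that this is drafting, with little practical effect. The third interval's start date stands directly beneath its heading, so a programmer who follows the dates would assign events correctly and only the table header would mislead. The boundary rule and the interval dates sit in different subsections joined by a dead reference, so combining them is an inference. All of this stands, and it limits the size of the point. It does not remove it: a wrong header is what the reader of the table sees, and the SAP offers no other intervals to which the rule could apply.

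A reader might infer more than the documents support.

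- *That the rule drops hypersensitivity events.* It is written only for malignancy and depression. SAP 4.6.2.1 states no such rule, and its labels include the upper limits, so hypersensitivity is affected only by the label.
- *That adverse events of special interest disappear from the report.* They do not. Overall frequency tables and by-patient listings for malignancy and depression are kept (SAP 4.6.2.4 and 4.6.2.5), as are the general adverse event summaries. Of the two categories that carry the rule, only malignancy is among the events of special interest in Protocol 8.3.6.
- *That a lost day is an infusion day.* The schedule in Protocol 1.3 starts at Day 1, so on a strict count its Day 84 is first injection + 83, which is assigned. On a week count, Week 12 is + 84. The visit also has a tolerance of 7 days either way. The documents do not fix an infusion on + 84, and they give no reason for malignancy or depression onset to cluster there.
- *That the person-time of the lost days stays in the denominator.* The SAP gives no formula for interval-specific person-time, so this cannot be determined.

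**Conclusion.** Both defects are real as written, and both are minor.

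The label error rests on SAP 4.6.2.1 alone. It puts 83 days, + 85 to + 167, under a heading of 24 weeks or later and leaves no interval labelled for over 12 to under 24 weeks. SAP 4.6.2.3 reports infections at 1, 6, 12 and 24 weeks, which fits a third interval that was meant to follow week 12.

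The boundary gap rests on one inference, that the malignancy and depression rule applies to the 4.6.2.1 dates. On that reading exactly two days, + 42 and + 84, belong to no interval. Only interval-specific rates and plots are affected, and under uniform onset the expected loss is 1 to 2% of events. The documents give no event counts from which a change in any particular rate could be calculated. The efficacy analyses are untouched.

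**What to change.** Four wording changes in the SAP:

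1. In 4.6.2.4 and 4.6.2.5, count an event if it starts or worsens on or after the interval start date and on or before the interval end date.
2. In 4.6.2.1, relabel the third interval as > 12 weeks, which matches its start at + 85 and its open end.
3. In 4.6.2.4 and 4.6.2.5, replace the reference to Section 6.14.2.1 with Section 4.6.2.1.
4. In 4.6.2.1, state the same assignment rule for hypersensitivity, so that one rule covers all three categories.

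The cost is a text edit. Data collection and study conduct do not change.
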